### **9.1.2.2. EuroQol Group Health Outcome Measure (5 level; EQ-5D-5L)**

The EQ-5D-5LTM is a trademark of the EuroQol Group® and is an instrument designed to assess decrements in health. The EQ-5D-5L includes a Visual Analog Scale (VAS) and a descriptive system that defines health in terms of 5 dimensions: Mobility, Self-Care, Usual Activities, Pain/Discomfort, and Anxiety/Depression. Each dimension has 5 response categories corresponding to the level of severity (i.e., no problems, slight problems, moderate problems, severe problems, and unable to/extreme problems). Subjects will complete the questionnaire according to the schedule in [Table 1](#). A sample of the EQ-5D-5L will be provided to study sites outside of this protocol.

### **9.1.3. Timed 25-Foot Walk**

The T25-FW [\[Kaufman 2000\]](#) is a reliable quantitative mobility and leg function performance test based on a timed 25-foot walk. The subject is directed to one end of a clearly marked 25-foot course and is instructed to walk 25 feet as quickly as possible, but safely. Subjects are allowed to use assistive devices (canes, crutches, walkers) as needed. The time is calculated from when the lead foot crosses the start point to when the subject has reached the 25-foot mark. The task is immediately administered again by having the subject walk back the same distance. The score for the T25-FW is the average of the 2 completed trials.

#### **9.1.3.1. Short Form 12 Health Survey**

Quality of life will be assessed using the 12-item Short-Form health survey Version 2 (SF-12v2) [\[Maruish 2012\]](#). Subjects will complete the questionnaire according to the schedule in [Table 1](#). A sample of the SF-12 will be provided to the study sites outside of this protocol.

#### **9.1.3.2. Columbia-Suicide Severity Rating Scale**

The C-SSRS is a clinician-administered instrument that assesses suicidal ideation and behavior [\[Posner 2011\]](#). The “Screening” version of the instrument will be administered to De Novo Subjects at the screening visit. The “Since Last Visit” version will be administered to all participating subjects at all other visits specified in [Table 1](#). A sample of the C-SSRS will be provided to the study sites outside of this protocol.

## **9.2. Pharmacokinetic Assessments**

PK samples will be collected from a subset of de novo subjects (approximately 50) enrolled at selected sites.

CONFIDENTIAL

The information contained herein may not be used, disclosed, or published without the written consent of Biogen MA Inc.

The following parameters, but are not limited to, will be calculated to assess the PK of ALKS 8700:

- Maximum observed concentration ( $C_{\max}$ )
- Time to reach  $C_{\max}$  ( $T_{\max}$ )
- $AUC_{\text{last}}$

Concentrations of analytes considered appropriate for further evaluation (e.g., MMF, RDC-6567, and RDC-8439) will be quantified in plasma samples collected for PK evaluation. See Section 12.5 for further details.

CONFIDENTIAL

The information contained herein may not be used, disclosed, or published without the written consent of Biogen MA Inc.

## 10. SAFETY ASSESSMENTS

See Section 1.3 for the timing of all safety assessments.

Tests and evaluations affecting primary endpoints and/or analyses may need to be repeated if the original results are lost or damaged. In these cases, subjects will be asked to return to the study site to have the evaluations repeated.

### 10.1. Clinical Safety Assessments

The following clinical assessments will be performed to evaluate the safety profile of ALK 8700:

- AEs and SAEs will be monitored continuously from the time a subject signs the ICF until the completion of the final study visit ([Table 1](#)) and additional follow-up, if required.
- Medical history.
- Physical examinations: A full physical examination and measurement of body height and weight will be performed at screening. For Rollover Subjects, height will be carried over from information recorded in the antecedent study in which they participated. All subjects will have brief, symptom-directed physical examinations and will be weighed at timepoints specified in [Table 1](#).
- Vital sign measurements (temperature, heart rate, systolic and diastolic blood pressure, and respiratory rate): Blood pressure, heart rate, and respiratory rate will be measured after the subject has been resting in a seated or supine position for at least 5 minutes. Consistent measurements and procedures should be used for all assessments ([Table 1](#)).
- 12-Lead ECGs will be performed after the subject has rested quietly for at least 5 minutes in the supine position. ECGs will be conducted using calibrated equipment and assessed by a qualified clinician ([Table 1](#)).
- C-SSRS administered by the clinician: The “Screening” version of the instrument will be administered to De Novo subjects at the Screening Visit. The “Since Last Visit” version will be administered to all subjects at all other visits specified in [Table 1](#).
- Concomitant therapy and procedure recording.

### 10.2. Laboratory Safety Assessments

Blood and urine samples for laboratory assessments will be collected at the timepoints specified in [Table 1](#). Specific hematology, biochemistry, and urinalysis assessments to evaluate the safety

CONFIDENTIAL

The information contained herein may not be used, disclosed, or published without the written consent of  
Biogen MA Inc.

profile of ALKS 8700 are listed in [Table 3](#). Samples will be collected in accordance with the site's usual procedures and analyzed by a central laboratory.

Samples will be analyzed using Good Laboratory Practice-validated assays.

**Table 3: Clinical Laboratory Assessments**

Hematology 	Biochemistry	Urinalysis
Hematocrit	Sodium	Color
Hemoglobin	Potassium	pH
Red blood cell count	Chloride	Specific gravity
Total and differential (absolute) white blood cell count	Bicarbonate	Ketones
Platelets	Glucose	Protein
	Thyroid-stimulating hormone (TSH) 	Glucose
	Calcium	Bilirubin
	Uric Acid	Nitrite
	Creatinine	Urobilinogen
	Total protein	Occult blood
	Blood urea nitrogen	Microscopic examination of sediment only if urinalysis dipstick results are abnormal
	Albumin	Urine albumin
	Total bilirubin	Urine beta-2-microglobulin
	Alanine aminotransferase (ALT)	Urine creatinine
	Aspartate aminotransferase (AST)	
	Lactic dehydrogenase (LDH)	
	Alkaline phosphatase	
	Creatine phosphokinase	
	Lipid profile: blood cholesterol, high-density lipoprotein, low density lipoprotein, and triglycerides	

 Additional hematology assessments will be collected for subjects requiring follow-up for lymphopenia at the time of study completion or early termination.

 To be assessed at screening only.

#### 10.2.1. Pregnancy Testing

A urine pregnancy test will be administered to all women regardless of childbearing potential at the timepoints specified in [Table 1](#). Results must be negative for initial study eligibility and continued participation.

CONFIDENTIAL

The information contained herein may not be used, disclosed, or published without the written consent of Biogen MA Inc.

### **10.2.2. Serology Testing**

A blood sample for a serology panel testing for hepatitis B surface antigen, hepatitis C antibody, and HIV antibody will be performed at screening only ([Table 1](#)).

CONFIDENTIAL

The information contained herein may not be used, disclosed, or published without the written consent of  
Biogen MA Inc.

## **11. SAFETY DEFINITIONS, RECORDING, REPORTING, AND RESPONSIBILITIES**

Throughout the course of the study, every effort must be made to remain alert to possible AEs. If an AE occurs, the first concern should be for the safety of the subject. If necessary, appropriate medical intervention should be provided.

At the signing of the ICF, each subject and/or his/her legally authorized representative and/or main caregiver must be given the names and telephone numbers of site staff for reporting SAEs, pregnancies, overdoses, and medical emergencies. Throughout the protocol, the Sponsor is named, but reporting may be done through a CRO.

### **11.1. Definitions**

#### **11.1.1. Adverse Event**

An AE is any untoward medical occurrence in a patient or clinical investigation subject (subject) administered a pharmaceutical product and that does not necessarily have a causal relationship with this treatment. An AE can therefore be any unfavorable and unintended sign (including an abnormal assessment such as an abnormal laboratory value), symptom, or disease temporally associated with the use of a medicinal (investigational) product, whether or not related to the medicinal (investigational) product.

Determination of whether an abnormal assessment (e.g., laboratory value, vital sign, and ECG) result meets the definition of an AE will be made by the Investigator. Abnormal results are not considered AEs unless one or more of the following criteria are met:

- The result meets the criteria for an SAE.
- The result requires the subject to receive specific corrective therapy.
- The result is considered by the Investigator to be clinically significant.

#### **11.1.2. Serious Adverse Event**

An SAE is any untoward medical occurrence that at any dose:

- Results in death.
- In the view of the Investigator, places the subject at immediate risk of death (a life-threatening event); however, this does not include an event that, had it occurred in a more severe form, might have caused death.
- Requires inpatient hospitalization or prolongation of existing hospitalization.
- Results in persistent or significant disability/incapacity.

CONFIDENTIAL

The information contained herein may not be used, disclosed, or published without the written consent of Biogen MA Inc.

- Results in a congenital anomaly/birth defect.
- Is a medically important event.

A medically important event is an AE that, in the opinion of the Investigator, may jeopardize the subject or may require intervention to prevent one of the other outcomes listed in the definition above. (Examples of such medical events include allergic bronchospasm requiring intensive treatment in an emergency room or convulsions occurring at home that do not require an inpatient hospitalization.)

### **11.1.3. Prescheduled or Elective Procedures or Routinely Scheduled Treatments**

A prescheduled or elective procedure or a routinely scheduled treatment will not be considered an SAE, even if the subject is hospitalized. The study site must document all the following:

- The prescheduled or elective procedure or routinely scheduled treatment was scheduled (or was on a waiting list to be scheduled) prior to obtaining the subject's consent to be in the study.
- The condition requiring the prescheduled or elective procedure or routinely scheduled treatment was present before and did not worsen or progress in the opinion of the Investigator between the subject's consent to be in the study and the time of the procedure or treatment.
- The prescheduled or elective procedure or routinely scheduled treatment is the sole reason for the intervention or hospital admission.
  - If a subject is hospitalized due to local requirements for administration of the study treatment, the hospitalization should not be considered an SAE unless one of the requirements in Section 11.1.2 is met.

## **11.2. Safety Classifications**

### **11.2.1. Investigator Assessment of Events**

All events must be assessed to determine the following:

- If the event meets the criteria for an SAE as defined in Section 11.1.2.
- The relationship of the event to study treatment as defined in Section 11.2.2.
- The severity of the event as defined in Section 11.2.3.

### **11.2.2. Relationship of Events to Study Treatment**

The following definitions should be considered when evaluating the relationship of AEs and SAEs to the study treatment.

CONFIDENTIAL

The information contained herein may not be used, disclosed, or published without the written consent of Biogen MA Inc.

Relationship	Criteria for assessment
Definitely related	
There is evidence of exposure to the test drug.
 
AND
 
The temporal sequence of the AE onset relative to administration of the test drug is reasonable.
 
The AE is more likely explained by the test drug than by another cause.
 
Dechallenge (if performed) is positive.
 
Rechallenge (if feasible) is positive.
 
The AE shows a pattern consistent with previous knowledge of the test drug or test drug class.

Probably related	
There is evidence of exposure to the test drug.
 
AND
 
The temporal sequence of the AE onset relative to administration of the test drug is reasonable.
 
The AE is more likely explained by the test drug than by another cause.
 
Dechallenge (if performed) is positive.

Possibly related	
There is evidence of exposure to the test drug.
 
AND
 
The temporal sequence of the AE onset relative to administration of the test drug is reasonable.
 
The AE could have been due to another equally likely cause.
 
Dechallenge (if performed) is positive.

Probably not related	
There is evidence of exposure to the test drug.
 
AND
 
There is another more likely cause of the AE.
 
Dechallenge (if performed) is negative or ambiguous.
 
Rechallenge (if performed) is negative or ambiguous.

Definitely not related	
The subject did not receive the test drug.
 
OR
 
Temporal sequence of the AE onset relative to administration of the test drug is not reasonable.
 
OR
 
There is another obvious cause of the AE.

CONFIDENTIAL

The information contained herein may not be used, disclosed, or published without the written consent of  
Biogen MA Inc.

### 11.2.3. Severity of Events

The following definitions should be considered when evaluating the severity of AEs and SAEs:

Severity of Event	
Mild	Symptoms barely noticeable to subject or does not make subject uncomfortable; does not influence performance or functioning; prescription drug not ordinarily needed for relief of symptoms but may be given because of personality of subject.
Moderate	Symptoms of a sufficient severity to make subject uncomfortable; performance of daily activity is influenced; subject is able to continue in study; treatment for symptoms may be needed.
Severe	Symptoms cause severe discomfort; symptoms cause incapacitation or significant impact on subject's daily life; severity may cause cessation of treatment with study treatment; treatment for symptoms may be given and/or subject hospitalized.

### 11.2.4. Expectedness of Events

Expectedness of all SAEs will be determined by the Sponsor according to the ALKS8700 Investigator's Brochure.

## 11.3. Monitoring and Recording Events

### 11.3.1. Adverse Events

Any AE experienced by the subject between the time of first dose of study treatment and until the completion of the safety follow-up visit (Visit 16) is to be recorded on the eCRF, regardless of the severity of the event or its relationship to study treatment. At each study visit, the Investigator will assess the subject for AEs and will record any new AEs or updates to previously reported AEs on the eCRF. Any AE or SAE having an onset after the safety follow-up visit will not be collected or reported unless the Investigator feels that the event may be related to the study treatment.

The following events will not be collected as AEs:

- Disability progression based on the EDSS is captured in the MS efficacy assessments and is not to be recorded as an AE unless the event meets the definition of an SAE (see Section 11.1.2). Events of MS relapse, whether protocol-defined or not, are to be recorded as AEs (or as SAEs [see Section 11.1.2]).
- Illnesses present prior to the subject signing the ICF are considered to be pre-existing conditions and are documented on the medical history eCRF. Pre-existing conditions that worsen during the study are entered on the AE eCRF.
- Pregnancy is not considered an AE, although a subject will be withdrawn from the study if a pregnancy occurs. As described in Section 11.4.1, the pregnancy must be reported to Biogen and additional follow-up may be required.

CONFIDENTIAL

The information contained herein may not be used, disclosed, or published without the written consent of Biogen MA Inc.

The Investigator will assess all AEs regarding any causal relationship to the study treatment (see Section 11.2.2), the severity of the event, action taken, and subject outcome.

The criteria set out in Section 11.2.3 should be used to guide the assessment of severity.

All AEs will be followed until resolution, until deemed stable by the Investigator, or until the subject is deemed by the Investigator to be lost to follow-up.

For clinical study safety reporting purposes, the version of the Investigator's Brochure at the time of the event occurrence will be used as the reference document to designate event expectedness.

Withdrawal from the study as a result of an AE and any therapeutic measures that are taken shall be at the discretion of the Investigator. If a subject withdraws from the study for any reason, any ongoing AEs will be followed until resolution, until deemed stable by the Investigator, or until the subject is deemed by the Investigator to be lost to follow-up.

### **11.3.2. Serious Adverse Events**

Any SAE experienced by the subject between the time of the signing of the ICF and until the completion of the safety follow-up visit (Visit 16) is to be recorded on an SAE form, regardless of the severity of the event or its relationship to study treatment. SAEs must be reported to the Sponsor within 24 hours as described in Section 11.3.3. Follow-up information regarding an SAE also must be reported within 24 hours.

Subjects will be followed for all SAEs until the completion of the safety follow-up visit (Visit 16). Thereafter, the event should be reported to the Sponsor only if the Investigator considers the SAE to be related to study treatment.

Any SAE that is ongoing when the subject completes or discontinues the study will be followed by the Investigator until the event has resolved, stabilized, or returned to baseline status.

### **11.3.3. Immediate Reporting of Serious Adverse Events**

In order to adhere to all applicable laws and regulations for reporting an SAE, the study site must formally notify the Sponsor within 24 hours of the site staff becoming aware of the SAE. It is the Investigator's responsibility to ensure that the SAE reporting information and procedures are used and followed appropriately.

CONFIDENTIAL

The information contained herein may not be used, disclosed, or published without the written consent of Biogen MA Inc.

### Reporting Information for SAEs

A report **must be submitted** to the Sponsor regardless of the following:

- Whether or not the subject has undergone study-related procedures
- Whether or not the subject has received study treatment
- The severity of the event
- The relationship of the event to study treatment

To report initial or follow-up information on an SAE, fax or email a completed SAE form; refer to the Study Reference Manual's Official Study Contact List for complete contact information.

#### 11.3.3.1. Deaths

Death is an outcome of an event. The event that resulted in death should be recorded on the appropriate eCRF. All causes of death must be reported as SAEs within 24 hours of the site becoming aware of the event. The Investigator should make every effort to obtain and send death certificates and autopsy reports to the Sponsor. The term death should be reported as an SAE only if the cause of death is not known and cannot be determined.

#### 11.3.4. Suspected Unexpected Serious Adverse Reactions

Suspected unexpected serious adverse reactions are SAEs that are unexpected and judged by the Investigator or the Sponsor to be related to the study treatment administered.

### 11.4. Procedures for Handling Special Situations

#### 11.4.1. Pregnancy

Subjects should not become pregnant or impregnate their partners during the study and for 90 days after their last dose of study treatment. If a female subject becomes pregnant, study treatment must be discontinued *immediately*.

The Investigator must report a pregnancy from first dose of study treatment to 90 days after that last dose of study treatment by faxing or emailing the appropriate form to the Sponsor within 24 hours of the site staff becoming aware of the pregnancy. Refer to the Study Reference Manual's Official Study Contact List for complete contact information. The Investigator or site staff must report the outcome of the pregnancy to the Sponsor. A pregnancy is not considered an AE and should not be recorded on the AE eCRF.

Congenital abnormalities and birth defects in the offspring of male or female subjects should be reported as an SAE if conception occurred during the study treatment period or within 90 days from their last dose of study treatment.

CONFIDENTIAL

The information contained herein may not be used, disclosed, or published without the written consent of Biogen MA Inc.

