#### 6.1.2. De Novo Subjects

In order to qualify for participation in this study, De Novo Subjects must meet all of the following criteria:

1. Is willing and able to provide informed consent.
2. Capable of understanding and complying with the protocol.
3. Agrees to use an acceptable method of contraception for the duration of the study and for 30 days after any study treatment administration or is surgically sterile or postmenopausal (see [Section 11.5](#)).
4. Male and female adults aged 18 to 65 years, inclusive, at screening.
5. Has a confirmed diagnosis of RRMS according to the revised 2010 McDonald criteria [[Polman 2011](#)].
6. EDSS score of 0.0-6.0 at screening and Visit 2.
7. Neurologically stable with no evidence of relapse within 30 days prior to Visit 2.

CONFIDENTIAL

The information contained herein may not be used, disclosed, or published without the written consent of Biogen MA Inc.

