## **6.2. Exclusion Criteria**

### **6.2.1. Rollover Subjects**

Rollover Subjects will be excluded from participation in this trial if they meet any of the following criteria:

1. Have any finding(s) that in the view of the Investigator or Medical Monitor would compromise the safety of the subject, affect their ability to adhere to the protocol visit schedule, or to fulfill visit requirements or make the subject unsuitable for participation in the study (including overall clinical assessment).
2. Subject is pregnant or breastfeeding or plans to become pregnant or begin breastfeeding at any point during the study and for 30 days after any study treatment administration.
3. Is employed by Biogen, contract research organization (CRO), or study site (permanent, temporary contract worker, or designee responsible for the conduct of the study) or is immediate family of a Biogen, CRO, or study site employee. Immediate family is defined as a spouse, parent, sibling, or child, whether biological or legally adopted.

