### **11.5. Contraception Requirements**

All male and female subjects must agree to the use of 2 methods of contraception for the duration of the study and 30 days after the final dose of study treatment. This includes at least 1 form of highly effective method of contraception and 1 acceptable method of contraception (and additional restrictions, if required, will be clarified in the locally approved ICF). Subjects who are abstinent are eligible, provided they agree to the use of 2 contraceptive methods (at least 1 being a highly effective method) should they become sexually active.

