#### **Highly effective methods may include:**

- Oral, intravaginal, or transdermal combined (estrogen and progestogen containing) hormonal contraception associated with inhibition of ovulation (oral contraceptives must have been initiated at least 30 days prior to screening)
- Oral, injectable, or implantable progestogen-only hormonal contraception associated with inhibition of ovulation (oral contraceptives must have been initiated at least 30 days prior to screening)
- Intrauterine device
- Intrauterine hormone-releasing system
- Bilateral tubal occlusion
- Vasectomized partner (provided that partner is sole sexual partner of subject and partner has received medical assessment of surgical success)

CONFIDENTIAL

The information contained herein may not be used, disclosed, or published without the written consent of Biogen MA Inc.

- Sexual abstinence (defined as refraining from heterosexual intercourse during the entire study period through at least 30 days after the final dose of study treatment)

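### Protocol 11.4.1 asks subjects to avoid conception for 90 days after the last dose, but the contraception and eligibility text stops at 30 days

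*Protocol*

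**What the plan says.** Protocol Section 11.4.1 opens with an instruction on subject conduct: "Subjects should not become pregnant or impregnate their partners during the study and for 90 days after their last dose of study treatment". It then uses the same 90 days for two other purposes. One is reporting: "The Investigator must report a pregnancy from first dose of study treatment to 90 days after that last dose of study treatment". The other is handling congenital abnormalities and birth defects as SAEs, which applies if conception occurred on treatment or "within 90 days from their last dose of study treatment".

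The sections that turn the conduct instruction into requirements use 30 days:

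- Section 11.5 requires of male and female subjects "2 methods of contraception for the duration of the study and 30 days after the final dose of study treatment". Where abstinence is the chosen method, it must last "through at least 30 days after the final dose of study treatment".
- Inclusion criterion 3, worded alike for Rollover Subjects (6.1.1) and De Novo Subjects (6.1.2), reads: "Agrees to use an acceptable method of contraception for the duration of the study and for 30 days after any study treatment administration". Surgically sterile and postmenopausal subjects are exempt.
- Exclusion criterion 2 for Rollover Subjects (6.2.1) and exclusion criterion 16 for De Novo Subjects (6.2.2) exclude a subject who is pregnant, or who plans a pregnancy "at any point during the study and for 30 days after any study treatment administration".

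Section 11.5 refers to 11.4.1 for pregnancy reporting but does not mention the different period. The SAP sets no post-dose period for conception or contraception.

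**The concern.** These are two rules on the same conduct. A subject can agree to criterion 3, pass the pregnancy-plan exclusion, use contraception exactly as Section 11.5 requires, and still intend to conceive two months after the last dose. Section 11.4.1 says that conception should not occur. A site that counsels from the eligibility criteria will tell subjects 30 days, and a site that counsels from the pregnancy section will tell them 90.

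What is at stake is the clarity of a safety instruction. Section 3.2.3.2 reports fetal vertebral malformations in rabbits but not in rats, so the protocol has a reason to address conception. For most subjects the period in question also begins after the last routine visit, so what they were told beforehand is what they will act on. No endpoint, analysis or sample size is affected.

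**Working it through.** The documents give no figure to reproduce. The check sets the periods side by side, subtracts, and then asks whether any other text closes the gap.

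| Provision | Section | Ends, in days after last dose | Kind of rule |
|---|---|---|---|
| Avoid pregnancy or impregnating a partner | 11.4.1 | 90 | Conduct |
| Two contraceptive methods | 11.5 | 30 | Conduct |
| Abstinence, if chosen | 11.5 | 30 (minimum) | Conduct |
| Inclusion criterion 3 | 6.1.1, 6.1.2 | 30 | Eligibility commitment |
| No planned pregnancy | 6.2.1, 6.2.2 | 30 | Eligibility, own pregnancy only |
| Report pregnancy | 11.4.1 | 90 | Surveillance |
| Birth defect as SAE, by conception date | 11.4.1 | 90 | Surveillance |

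**Size of the gap.** 90 - 30 = 60 days, that is, days 31 to 90 after the last dose.

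**On the study calendar**, assuming a last dose on Day 673 (nominal Visit 15, Week 96):

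- Visit 16: Day 687, which is 687 - 673 = 14 days after the last dose.
- 30-day commitments end: 673 + 30 = Day 703.
- No-conception instruction ends: 673 + 90 = Day 763.
- Uncovered: Days 704 to 763, and 763 - 703 = 60 days.

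**Does the phrase about the duration of the study close the gap?** The 30-day rules also run for the study's duration, so a long enough study would extend them. Section 5.2 classes a subject as completing the study at the follow-up visit, and Section 5.5 treats Visit 16 as the last study visit. At 14 days after the last dose it falls inside the 30 days and adds nothing. The same holds after early termination if the termination visit falls close to the last dose, because Visit 16 again follows 2 weeks later.

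**Subjects in lymphocyte monitoring.** Those with a last count below 0.8 x 10^3/µL may have visits 2, 4 and 6 months after Visit 16 (Protocol Table 2). Suppose these counted as part of the study, and take a month as 30 days:

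- Followed to the first monitoring visit only: 14 + 60 = day 74 after the last dose, leaving 90 - 74 = 16 days uncovered (9 to 23 with the ±7-day visit window).
- Followed to the second: 14 + 120 = day 134, past day 90, so no gap.

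The protocol does not say whether these visits count. For these subjects the gap is therefore somewhere between 0 and 60 days, depending on the reading.

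**The case against.** The strongest objection is that a protocol may properly follow pregnancies for longer than it requires contraception. That is right, and it disposes of part of what a reader might infer. The reporting window and the birth-defect SAE window in 11.4.1 are surveillance periods. That they outlast the 30-day contraception period is not a contradiction, and they need not be shortened to match it. The objection does not reach the first sentence of 11.4.1, which is about what subjects do, not what sites report.

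A second objection is that 60 days does not hold for everyone. This also stands in part. Surgically sterile and postmenopausal subjects are unaffected. The pregnancy-plan exclusions concern the subject's own pregnancy, so for men the mismatch rests on criterion 3 and Section 11.5 alone. Section 5.2 allows a subject's end-of-study date to be a last protocol-specified assessment or the resolution of an ongoing AE, so for some subjects the study may run past Visit 16. These points limit who is affected. They do not remove the mismatch for a subject whose study ends at Visit 16.

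A third is that 11.4.1 says only that subjects should not conceive, which is softer than a prohibition. That is fair, but an instruction in those terms still needs to agree with the requirements meant to carry it out.

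**Conclusion.** The inconsistency is real and lies in the current Version 5.0 text. One sentence of Section 11.4.1 sets 90 days for avoiding conception, while Section 11.5, inclusion criterion 3 and the pregnancy-plan exclusions set 30. For a non-exempt subject whose study ends at Visit 16, the instruction stands without a matching contraception or eligibility commitment for 60 days. The calendar dates assume a last dose on Day 673; the 60 days do not depend on that.

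Three stronger readings are tempting and are not supported:

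- *That two thirds of an at-risk period goes unprotected.* This takes 90 days to be the true risk period. The documents do not say so. The rabbit finding is not tied to any interval after dosing, and the same section reports no notable fertility or embryonic findings in the rat fertility studies.
- *That nothing asks subjects to avoid pregnancy on days 31 to 90.* Section 11.4.1 does ask it. What is missing is a required method and a commitment at entry.
- *That subjects have been given conflicting instructions.* The consent form is not among the documents, and Section 11.5 leaves room for further restrictions in the locally approved form. What can be shown is that the protocol gives sites two statements.

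The documents do not show which period was intended.

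**What to change.** Reconcile the no-conception sentence in Section 11.4.1 with Sections 6.1.1, 6.1.2, 6.2.1, 6.2.2 and 11.5, including the abstinence definition, so that sites give one post-dose instruction on avoiding conception. The sponsor decides the period; none is proposed here. The pregnancy-reporting and birth-defect SAE windows may stay as they are.

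In the same edit, state whether lymphocyte-monitoring visits count as part of the duration of the study for the contraception rule. Then check the consent form, including local versions, against the reconciled text.

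The cost is protocol wording, and consent wording if that check finds a difference. No data collection, analysis or sample size changes.
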